8.4.2 Collection, Recording and Reporting of Serious Adverse Events

SAE Reporting by the Investigator

All SAEs must be reported **immediately** as soon as it becomes known to the Investigator and not later than within 24 hours of their knowledge of the occurrence of an SAE.

TKL Pharmacovigilance Group
[name]
TKL Research, Inc.
[contact], [name]
[contact]
[contact]
[contact]

The Investigator will complete the eCRF SAE report Form with the fullest possible details **within 3 calendar days** of the Investigator's knowledge of the SAE.

Additional information relevant to the SAE such as hospital records, results from investigations, e.g., laboratory parameters (that are not already uploaded in the eCRF), invasive procedures, scans and x-rays, and autopsy results can be faxed or scanned and e-mailed to TKL using the contact details in the section above. In any case this information must be supplied by the Investigator upon

request from TKL. On any copies provided, such details such as subject's name, address, and hospital ID number should be redacted, and the subject number provided, instead.

The Investigator will supply TKL and the institutional review board (IRB) with any additional requested information such as results of post-mortem examinations and hospital records.

Completion of the Demographics, AE Log, Medical History Log and Concomitant Medication Log are mandatory for initial reports and for follow-up reports if any relevant changes have been made since the initial report.

Expedited Reporting

TKL will report all SAEs to Amzell B.V. as per the protocol-specific SAE flow procedures.

Any AEs that are **serious, unexpected, and with a reasonable possible causality to the IMP**, as judged by either the Investigator or Amzell B.V., will be reported to regulatory authorities in US and to IRB within the stipulated timelines. Full details on the reporting procedures, responsibilities, and personnel are presented in the Safety Management Plan (SMP).

The expectedness is assessed by Amzell B.V.

SAEs will be considered reportable regardless of whether or not the IMP was used in accordance with the provisions in the protocol.

8.5 Follow-up of Adverse Events and Serious Adverse Events

8.5.1 Follow-up of Adverse Events with Onset during the Study

During the study, the Investigator must follow-up on each AE until it is resolved or until the medical condition of the subject is stable.

After the subject's last visit, the Investigator must follow-up on any AEs that occurred during the study classified as serious or considered to have a reasonable possible causality to the IMP with the outcome "Not recovered" until resolved or until the medical condition of the subject is stable. All such relevant follow-up information must be reported to Amzell B.V. If the event is a chronic condition, the Investigator and Amzell B.V. may agree that further follow-up is not required.

Collection of SAEs with Onset after Last Visit

If an Investigator becomes aware of a SAE after the subject's last visit and assesses the SAE to have a reasonable possible causality to the IMP, the case will have to be reported to Amzell B.V., regardless how long after the end of the study this takes place. Such reports will be considered for expedited reporting and managed as such.

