There is evidence or argument to suggest a causal relationship between the IMP and the AE. The AE may occur as part of the pharmacological action of the IMP or may be unpredictable in its occurrence.

Examples:

- adverse events that are uncommon but are known to be strongly associated with IMP exposure.
- adverse events that are not commonly associated with IMP exposure, but the event occurs in association with other factors strongly suggesting causation, such as a strong temporal association or the event recurs on rechallenge.

No reasonable possibility:

- There is no reasonable evidence or argument to suggest a causal relationship between the IMP and the AE.

Examples:

- known consequences of the underlying disease or condition under investigation.
- adverse events common in the study population, which are also anticipated to occur with some frequency during the course of the study, regardless of IMP exposure.

Action Taken with IMP

The action taken with the IMP in response to an AE must be classified as one of the following:

- No change (medication schedule maintained or no action taken)
- Withdrawn
- Interrupted

Other Action Taken

Adverse events requiring therapy must be treated with recognized standards of medical care to protect the health and well-being of the subject. Appropriate resuscitation equipment and medicines must be available to ensure the best possible treatment for an emergency situation.

If medication is administered to treat the AE, this medication should be entered in the eCRF.

Date and Time of Outcome

The date and time (time can be omitted, if applicable) the subject recovered or died. If outcome is “Not recovered” or “Recovering” no date of outcome can be recorded.

Outcome

The outcome of an AE must be classified as one of the following:

- Recovered (fully recovered or the condition has returned to the level observed at initiation of study treatment)
- Recovered with sequelae (resulted in persistent or significant disability/incapacity)
- Recovering
- Not recovered
- Fatal

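### The rule for following adverse events after the last visit names only 'Not recovered' and leaves out 'Recovering', the protocol's other unresolved outcome

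*Protocol*

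**What the plan says.** Protocol section 8.2.2 fixes how an AE outcome is coded: "The outcome of an AE must be classified as one of the following", and five categories follow: Recovered, Recovered with sequelae, Recovering, Not recovered, and Fatal. The same section sets a rule for the outcome date: "If outcome is “Not recovered” or “Recovering” no date of outcome can be recorded".

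Protocol section 8.5.1 then sets two follow-up duties.

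- Up to the last visit: "During the study, the Investigator must follow-up on each AE until it is resolved or until the medical condition of the subject is stable". No outcome code is mentioned.
- After the last visit: the duty is limited to AEs with onset during the study that are serious or possibly related to the product "with the outcome 'Not recovered' until resolved or until the medical condition of the subject is stable". The follow-up information goes to the sponsor. For a chronic condition, investigator and sponsor may agree to stop.

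SAP section 10.6 lists the AE outcome and gives a convention for missing outcomes. It contains no follow-up rule.

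**The concern.** The follow-up rule uses one coded outcome where the coding scheme has two that mean the event is not over. While the subject is in the study, every AE is followed whatever its code. After the last visit, whether follow-up is still required depends on which of the two unresolved codes the site chose. The protocol gives no reason for treating them differently.

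What is at stake is the completeness of final AE outcomes. Safety and tolerability are a secondary objective (section 2.1.2). Skin scores of 2 or more and clinically significant laboratory findings count as AEs (sections 7.2.5 and 7.2.2.1). Such events, if improving but not yet resolved, are the ones a site would naturally code 'Recovering'.

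**Working it through.** No arithmetic bears on the wording itself. The check sets the outcome list beside the follow-up rule and then looks for any other text that fills the gap.

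**Step 1. Which outcomes are unresolved?**

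| Outcome (8.2.2) | Outcome date possible? | Resolved? | Named in the rule for after the last visit (8.5.1)? |
|---|---|---|---|
| Recovered | Yes | Yes | Not needed |
| Recovered with sequelae | Yes | Yes | Not needed |
| Fatal | Yes | Closed | Not needed |
| Not recovered | No | No | Yes |
| Recovering | No | No | **No** |

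'Recovered' is defined in 8.2.2 as full recovery or return to the level at the start of study treatment, so an event coded 'Recovering' has not met it. Each AE takes one code only, so 'Recovering' cannot be read as a kind of 'Not recovered'. Section 8.5.1 puts the outcome in quotation marks exactly as it stands in the code list, which points to the code rather than to a loose word for unresolved.

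**Step 2. Which AEs does the condition limit?** The sentence can be parsed in two ways.

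- The outcome condition limits both serious and related AEs (the more natural reading). The gap then covers serious AEs and related AEs coded 'Recovering'.
- The condition limits only related AEs. Serious AEs are then followed whatever their outcome code, and the gap covers non-serious related AEs coded 'Recovering'.

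A gap remains on either reading.

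**Step 3. Does other text fill it?**

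- Section 8.5.1, last paragraph: headed for serious events with onset after the last visit, so not for ongoing events.
- Section 8.4.2: the investigator supplies further information on a serious AE when asked. That is not a standing duty, and it does not reach non-serious related AEs.
- Section 8.2.1: monitoring of the subject's health runs to the last visit.
- Section 8.1: the post-treatment window (last visit or 3 weeks post dose, whichever is longer) classifies AEs by time of onset. It does not require follow-up of an ongoing one.
- Section 4.4: follow-up examinations are required at discontinuation, without saying how an unresolved AE is then followed.
- Section 9.7.6.2 and SAP section 10.6: a missing outcome without an outcome date is taken as not recovered. An entered 'Recovering' stays as entered.
- Section 9.7.6: refers to a Safety Management Plan for monitoring and follow-up. It is not among the documents.

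**Step 4. Who is exposed?** Completers have outpatient visits at 21, 28 and 35 days after the last application (Table 2), each collecting AEs. Their last visit is at 35 days, against the 5 days of residual drug effect in section 8.1: 35 − 5 = 30 days later. Few related AEs should still be 'Recovering' by then. For early withdrawals, footnote E of Table 1 lists assessments to attempt at withdrawal, while the Table 2 visits are scheduled after Period 3. Their last visit may therefore fall soon after dosing stops.

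**The case against.** The strongest case on the other side has five parts.

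1. *The sections do not contradict each other.* Section 8.2.2 governs data entry and 8.5.1 governs the scope of follow-up. A scope narrower than the set of undated outcomes can coexist with the date rule. This stands: a reader might infer a contradiction, but the documents show a mismatch, with one unresolved category left out and no reason given.
2. *Nothing tells a site to abandon the event.* This stands. A reader might infer that 'Recovering' events are dropped or that their outcome is never obtained. The text only ceases to require follow-up; it does not forbid it. Nor would adding 'Recovering' guarantee capture of a later relapse, since follow-up of 'Not recovered' events also ends at stability.
3. *The Safety Management Plan may hold the detail.* Section 9.7.6 says that plan sets out how follow-up is done. This stands as a limit on confidence. It does not remove the point, because 8.5.1 states an explicit rule of its own that a site would apply as written.
4. *Serious AEs may already be covered.* This stands as a possible reading of the sentence, so the gap for serious AEs is likely rather than certain.
5. *The effect is minor.* In healthy subjects using a topical gel, related or serious AEs unresolved at the last visit may be few. The planned AE incidence tables do not depend on follow-up after the last visit. This stands for size; it does not explain the omission.

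**Conclusion.** The point holds as a mismatch between the outcome list in 8.2.2 and the follow-up rule in 8.5.1. Two outcomes are unresolved, and the rule for after the last visit names one. Followed as written, the protocol requires no follow-up to resolution or stability for a related AE coded 'Recovering' at the last visit and, on the more natural reading, none for a serious AE so coded. This rests on the protocol and SAP alone; the Safety Management Plan could narrow or close the gap.

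The documents give no rate from which the number of affected AEs could be estimated. A reader might take the 20% allowance in section 9.1 (0.20 × 75 = 15 subjects) as the number at risk. That is not supported: the allowance also includes non-evaluable subjects, who may complete every visit; it is a planning assumption rather than a cap, since section 4.5 replaces subjects withdrawn after first dosing; and it counts subjects, not AEs that are serious or related and coded 'Recovering'. The number is probably small for completers, and early withdrawals are more exposed. The primary pharmacokinetic comparison, the sample size and the error rates are unaffected. The change is worth making because the omission is plain and the remedy cheap.

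**What to change.** Reconcile 8.5.1 with the outcome list in 8.2.2. The rule for after the last visit should apply to any AE with onset during the study that (a) has the outcome 'Not recovered' or 'Recovering' and (b) is either serious or rated as having a reasonable possibility of a causal relationship. Setting the two conditions out separately, as here, also removes the doubt about whether the outcome condition applies to serious AEs. The existing end points (resolution, stability, or agreement on a chronic condition) can stay as they are. Check that the Safety Management Plan uses the same wording.

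The cost is a short rewording of one sentence and possibly a few extra follow-up contacts. The SAP needs no change.

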9. STATISTICAL METHODS

Additional details of the proposed statistical analysis methods will be documented in the Statistical Analysis Plan (SAP), which will be written following finalization of the protocol and prior to study unblinding/analysis (as appropriate). This section is a summary of the planned statistical analyses of the most important endpoints including primary and key secondary endpoints. The SAP creation and statistical analysis will be performed by Lead Statistician ([Guidance for Industry Bioavailability and Bioequivalence Studies Submitted in NDAs or INDs-General Considerations, March 2014](#)).

All concentration and PK data will be listed. This includes any data for subjects who are not included in the analysis (e.g., subjects withdrawn from the study due to AEs).

9.1 Determination of Sample Size

Based on the assumption (averaging historical data and Phase 1 Study 000084 study results), intra-subject coefficient of variation (CV) was 61%. A total of sixty (60) evaluable subjects will achieve 80% power using 95% confidence interval (CI), to account for multiplicity. The true ratio that was used in the sample size calculation was 1.05. Enough healthy adults will be screened to randomize approximately seventy-five (75) subjects to ensure sixty (60) evaluable subjects, assuming a 20% dropout and non-evaluable rate. All subjects will receive all 3 treatments over the course of the 3 study periods. Subjects will be randomized to one of the 6 possible sequences of 3 treatments, as specified in the design in [Figure 1](#), to provide adequate information about the PK parameters and safety for the purposes of this study.

9.2 Subject Disposition

All healthy subjects screened and enrolled will be followed to completion. All subjects should be included in the analysis unless prespecified in the protocol e.g., PK parameters can be derived or major deviations that impact PK as described below. The subjects screened but not found eligible will be included in the study report but not study analysis.

9.3 Protocol Deviations

Major protocol violations, such as significant non-compliance or other serious unforeseen violations deemed to invalidate the data collected for the purpose of the study will lead to exclusion of the data from analysis. In case of minor protocol violations, data will not be excluded from the data analysis. The rating of protocol violations as either ‘minor’ or ‘major’ will be decided on the basis of a review of the data before declaration of the ‘clean file’ and lock of database.

9.4 Statistical Analysis Sets (or Populations)

9.4.1 Safety Population

The safety population will include randomized subjects who received at least one dose of AMZ001 or Voltaren Arthritis Pain Gel. The randomized population will be used for safety analysis,

presentation of compliance and all baseline characteristics (demographics, medical history, prior and concomitant medication, and physical examination).

9.4.2 Pharmacokinetic (PK) Population

The PK population is defined as all randomized subjects who have at least one post-dose PK value, and who have no major protocol deviations concerning PKs.

9.4.3 PK Analysis Set

Two pharmacokinetic analysis sets (PKAS1 and PKAS2) will be considered for this clinical trial.

PKAS1 includes all subjects of the PK population, for which the relevant PK parameters (at least area under the plasma concentration-time curve from time zero to time to $[AUC_{0-t}]$ or C_{max}) can be derived for the reference treatment along with at least one of AMZ001 test products, 6 mL or 8 mL, regardless of baseline diclofenac concentration of the individual C_{max} in the relevant periods. This analysis set will be used in PK summaries and the primary analysis and the secondary PK analysis.

PKAS2 includes all subjects of the PK population, for which the relevant PK parameters (at least AUC_{0-t} or C_{max}) can be derived for the reference treatment along with at least one of AMZ001 test products, 6 mL or 8 mL, and with baseline concentration $\leq 5\%$ of the individual C_{max} in the relevant periods. This analysis set will be used for sensitivity analysis (and perform same analysis as PKAS1).

9.5 Study Population

9.5.1 Demographics and other Baseline Characteristics

Descriptive statistics from the randomized population will be used to summarize the baseline demographic information. For continuous variables, data will be presented by descriptive statistics (e.g., number, mean, median, standard deviation, medians, and range). For categorical variables, these data will be presented as counts and percentages.

Missing values will not be imputed.

9.5.2 Medical History, Concomitant Medication and Physical Examination

Medical history and concomitant medication will be presented in by-subject listings for the randomized population.

9.6 Treatment Compliance

Treatment compliance will be presented from the safety population.

9.7 Endpoint Assessments

9.7.1 General Considerations

Descriptive statistics will be used to summarize these study data. For continuous variables, data will be presented by descriptive statistics (e.g., number, mean, median, standard deviation,

medians, and range). For categorical variables, these data will be presented as counts and percentages.

Missing values will not be imputed.

9.7.2 Pharmacokinetics (PK)

PK analysis will be performed using the SAS® system. PK parameters assessed at Day 1 and Day 7 will include $AUC_{0-\tau}$, C_{max} , C_{min} , C_{av} , PTF, T_{max} , T_{min} , λ_z , and $T_{1/2}$, and will be presented in listings for individual subjects and summarized in tables and figures.

PK parameters $AUC_{0-\tau}$ and C_{max} will be compared across treatment groups using an analysis of variance (ANOVA) model. The ratio of the PK parameters will be estimated along with 90% confidence limits to assess comparable bioavailability.

Please refer to the SAP for detailed analysis method.

9.7.3 Primary Endpoint

Compare the exposure to diclofenac sodium, as measured by plasma concentration, AUC_{0-24} and C_{max} at steady state between two different dose levels of AMZ001 and one dose level of Voltaren Arthritis Pain Gel in healthy subjects on Day 7.

9.7.4 Secondary Endpoint(s)

The PK parameters C_{max} , C_{min} , T_{max} , T_{min} , λ_z , $T_{1/2}$, C_{av} and PTF of the two different dose levels of AMZ001 and the one dose level of Voltaren Arthritis Pain Gel will be calculated. The PK parameters for Day 1 will also be calculated and considered as secondary endpoints.

9.7.5 Safety Endpoint(s)

Adverse events (AEs) including serious, treatment emergent, adverse drug reactions (ADRs)

Local and systemic tolerability

9.7.5.1 Vital signs

Vital signs (blood pressure, pulse rate, and body temperature) will be summarized.

9.7.5.2 Clinical chemistry, hematology and urinalysis

Change from baseline of clinical chemistry, hematology and urinalysis parameters will be summarized.

9.7.6 Adverse Events (AEs)

A SMP is created to specifically identify how safety of the subjects will be monitored and follow-up will be performed for the study. The SMP is summarized below.

AEs will be coded according to the latest version of the Medical Dictionary for Regulatory Activities (MedDRA) and grouped by system organ class (SOC). All data will be listed by subject.

Only TEAEs will be presented in summary tables. Separate data listing will be provided for AEs that are defined as pre-treatment or post-treatment emergent.

9.7.6.1 Overview of Treatment Emergent Adverse Events (TEAEs)

A TEAE summary table will be presented including for each treatment the number of subjects reporting an AE, the percentage of subjects with an AE, and the number of events reported, for the following categories:

- All AEs
- Severe adverse events
- SAEs
- ADRs
- AEs leading to subject withdrawal.
- Death

AEs classified as a reasonable possibility are categorized as related to the IMP and are defined as ADRs.

9.7.6.2 Incidence of TEAEs

Summary tables will be prepared for the incidence of TEAEs per treatment by MedDRA SOC and preferred term, presenting number of subjects reporting an AE, the percentage of subjects (%) with an AE, and the number of events reported. Summary tables will be prepared for:

- All TEAEs
- AEs by causality
- AEs by intensity
- ADRs by intensity

Missing values will be treated as missing except for causality, intensity, seriousness, and outcome of an AE, at which occurrence a “worst case” approach will be taken. Thus, if causality is missing the AE will be regarded as related to the IMP, if the intensity is missing the intensity of the AE will be regarded as severe, if seriousness is missing the AE will be regarded as an SAE, and if the outcome is missing and no date of outcome is present the outcome is regarded as “not recovered”.

9.7.6.3 Serious adverse events and other significant adverse events

Separate listings will be provided for SAEs and other significant AEs.

9.7.6.4 Application site reactions

Assessments of application site reactions will be summarized by dose over the assessment time.

9.7.6.5 Physical examination

Physical examination will be listed by subject.

9.8 Interim Analyses

No interim analyses are planned.

9.9 Exclusion of Data from Analysis

Refer to Statistical Analysis Plan for details.

9.10 Handling of Dropouts and Missing Data

Refer to Statistical Analysis Plan for details.

10. DATA HANDLING AND RECORD KEEPING

10.1 Recording of Data

Data will be recorded via electronic data capture (EDC) and e-source direct data capture (DDC). Electronic Case Report Forms (eCRFs), which will be designed to identify each subject by randomization number and, where appropriate, subject's initials, the product being evaluated, study visit parameters to be measured or collected and the results observed. All entries to the eCRFs must be made as instructed by Amzell B.V. at study initiation.

The PI must sign the designated page(s) of the eCRFs, thereby stating that he/she takes responsibility for the accuracy of the data in the entire eCRF. All records will be kept in conformance to applicable national laws and regulations.

The copy of signed electronic informed consent form (eICF) will be included in each subject's file. When the study treatment is completed, the eICF will be kept in the appropriate file folder; otherwise, a note indicating where the records can be located will be made.

In addition to the eCRFs, individual subject e-source DDC files will be maintained. These documents may include the visit dates, the clinical study number, the name or initials of the subject, medical history or previous physical examinations, demographic and medical information, including laboratory data, skin assessments, concomitant medications/treatments, etc., any AEs encountered, and other notes, as appropriate.

